3. METHODOLOGY

3.1 Study design and setting

The study design will be a multicenter randomized-controlled trial in 3 tertiary care hospitals including Ramathibodi Hospital, Phramongkutklao Hospital and Rajavithi Hospital.

3.1.1 Ramathibodi Hospital is a [university hospital](#) of the Faculty of Medicine Ramathibodi Hospital which is a faculty within [Mahidol University](#) and the fourth oldest medical school in Thailand. The hospital serves at least 5,000 out-patient visits per day and in-patients with more than 1,000 beds for tertiary medical care. The hospital provides approximately 3,000 antenatal care service and delivery each year. It will be the primary site of the research investigation. The study will initiate here in June 2016 and followed by other centers. The study will take approximately 2 years for the accrual time to achieve the target number of participants and another year for the completion and analysis.

3.1.2 Phramongkutklao College of Medicine is the first and only medical cadet school in [Thailand](#). The college is the seventh medical school established in Thailand by the will of [King Bhumibhol Adulyadej](#). Phramongkutklao College of Medicine is an affiliated college of [Mahidol University](#). It is the teaching hospital accommodating 1,200-bed in the tertiary level. The hospital provides approximately 3,000 antenatal care service and delivery each year. The research will start soon after the study initiation in Ramathibodi Hospital once the ethics committee and funding are approved. The study will take approximately 2 years for the accrual time to achieve the target number of participants and another year for the completion and analysis.

3.1.3 Rajavithi Hospital is a 1,200-bed medical center accommodating 40,000 in-patients and 1,000,000 out-patients yearly or a daily average of 4,000 patients, with 200,000 referral patients (both in and out patients). The hospital provides medical service at standard health promotion in tertiary levels and above, including quality referral system. The hospital provides approximately 4,000 antenatal care service and delivery each year. The research will start soon after the study initiation in Ramathibodi Hospital once the ethics committee and funding are approved. The study will take approximately 2 years for the accrual time to achieve the target number of participants and another year for the completion and analysis.

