3.2.1 Inclusion criteria (ALL criteria)

- Singleton pregnant women age ≥ 18 years without significant medical conditions such as immunocompromised status, chronic infection (HIV infection, tuberculosis), chronic lung and cardiac conditions, chronic kidney disease, thyroid disease, or neuromuscular disease.
- Pregnant women attending the 1st antenatal care and intending to deliver at one of the study hospitals with gestational age < 16 weeks
- Thai nationality with ability to use Thai language proficiently both in spoken and written language.
- Have been diagnosed as high-risk pregnancy by obstetricians by having any of the following conditions

- a. Chronic hypertension prior to pregnancy
- b. Hypertension during pregnancy before 20week gestation.
- c. Pre-eclampsia/gestational hypertension during recent pregnancy
- d. Obesity defined by pre-pregnancy body mass index (BMI) ≥ 27.5 kg/m²
- e. Having diabetes mellitus or history of gestational diabetes in previous pregnancy
- Having SDB by either definition
 - a) RDI ≥ 5 events/hour by sleep testing at either point of testing during early pregnancy (0-16 GA week) or late pregnancy (GA 24-28 week)
 - b) OR Presence of snoring (either as frequent snoring ≥ 3 times/week or loud snoring) prior to or occurring during pregnancy
- Sign written informed consent

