3.3 Randomization and allocation

A randomization list will be generated and stratified by trimesters. For each stratum, a block randomization with varying block size from 4 to 8.

Preparation of randomization will be done by a third party, not involved in the clinical trial. Randomization sequence codes were generated using centralized computer system. Once eligible participants had agreed to participate the study and signed informed consent, the investigators entered clinical details into the system. Then the computer system generated the automatic randomization sequence and immediately sent back to the investigators for further allocation accordingly. After randomization and allocation, participants in the CPAP intervention group received CPAP treatment nightly throughout pregnancy until delivery.

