3.10.4 Statistical analysis

- Baseline demographic and clinical variables will be summarized using mean and its standard deviation (SD) or median and inter-quartile range as appropriate for continuous data, whereas categorical variables are summarized in frequencies and percentage. Comparisons of baseline characteristics between the 2 groups will be performed using t-test for the continuous variables and χ^2 test for the categorical variables.

- A blinded evaluation is planned to assess the observed primary end point by a clinical outcome assessment committee.
- The null hypothesis of the primary outcome for the Δ change of blood pressure (DBP) between treatment and controls are tested at 2-sided significant level of p -value <0.05 using t -test.
- Analyses for repeated measurement of secondary outcomes for continuous variables such as 24-hour blood monitoring, glucose level, Uterine artery Doppler ultrasound pulsatile index, estimated fetal growth, at 6-8 weeks after randomization, and during 2-3rd trimesters compared to baseline are performed using a longitudinal data analyses with linear mixed model.
- Analyses of secondary outcome of categorical data such as composite outcome 1 to 3, and individual outcome, control of BP, or non-dipping BP pattern will be compared between CPAP and control groups using χ^2 test, or Fisher exact test as appropriate.
- Gestational diabetes, as one of the inclusion criteria, was not included in endpoint analyses as initially planned.
- Predictors for composite outcome, and individual outcomes will be analyzed with multivariate logistic regression model adjusting for other co-variates.
- Statistical analyses will be performed according to the intention-to-treat analysis. Per-protocol analysis will then be analyzed for the comparisons of the results.

- In addition, per-protocol (PPA) and as-treated analyses (ATA) with counterfactual approach were also applied to deal with protocol violation using instrumental variable regression.
- We did not apply imputation for missing data because they were not used for the analysis.
- All statistical analyses are considered significant at the threshold level of 2-sided p-value < 0.05. Statistical analyses are performed using STATA Version 13.1 (StataCorp, College Station, TX).
- Interim analysis was not performed as initially planned, due to lower than expected number of deliveries when 50% of enrollments were achieved. Decisions were reported to the Ethic committee for approval.

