### **3.3 Randomization and allocation**

A randomization list will be generated and stratified by collaborative center. For each stratum, a block randomization with varying block size from 4 to 8 will be performed using computerized program by STATA.

Preparation of randomization will be done by a third party, not involved in the clinical trial. The randomized code will be sealed into the sequentially numbered, opaque sealed envelopes (SNOSE) and send to each collaborative center. Investigators enrolling the patients will not be aware of the order of the randomization until opening the envelope for subject allocation.

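### Randomisation is blocked within strata, but no stated treatment comparison uses the stratification factor; naming it in the analysis costs nothing and can recover a little power

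*Protocol*

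**What the plan says.** **Design.** Section 3.3 of the Protocol states: "A randomization list will be generated and stratified by trimesters". Section 3.3 of the Combined protocol and SAP states: "A randomization list will be generated and stratified by collaborative center". The Protocol allocates within each stratum by "block randomization with varying block size from 4 to 8", and the other document uses the same block sizes. Section 3.1 describes three tertiary hospitals.

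**Analysis.** Section 3.10.4 covers "Analyses of secondary outcome of categorical data such as composite outcome 1 to 3, and individual outcome, control of BP, or non-dipping BP pattern" with a chi-square "test, or Fisher exact test as appropriate". The primary change in DBP is tested with a t-test at two-sided 0.05. The Combined protocol and SAP has the same two tests. Neither document names a stratified test or a stratum term for any comparison of the arms.

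**Regression.** Section 3.10.4 also says that predictors of the composite and individual outcomes "will be analyzed with multivariate logistic regression model adjusting for other co-variates". It lists no covariates and does not mention the stratification factor.

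**The concern.** Blocking within strata makes the two arms nearly identical in stratum mix. If event risk differs between strata, the difference between arms then varies less from trial to trial than a pooled test assumes. The pooled test keeps a variance component that the design has removed. Its true type I error falls below 5% and it gives up some power.

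The composites carry the part of the research question about maternal and fetal complications, so avoidable loss there is worth removing. The same reasoning applies to the t-test on the primary outcome, to the extent that DBP change differs by stratum.

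**Working it through.** **1. The plan's own power figure.** Section 3.9.2 states power of 0.83 and 0.97 for differences of 12 and 15 points in composite 2 with 306 women (153 per arm). The control rate is 21.4% (812/3787, Secondary outcome section of the Combined protocol and SAP). The unstratified formula is

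Φ{[d − 1.96·√(2p̄(1−p̄)/n)] / √[(p₁(1−p₁) + p₂(1−p₂))/n]}.

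- 21.4% vs 9.4%: p̄ = 0.154; (0.120 − 1.96 × 0.0413)/0.0407 = 0.96; power 0.832.
- 21.4% vs 6.4%: p̄ = 0.139; (0.150 − 1.96 × 0.0396)/0.0386 = 1.88; power 0.970.

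Both match, so the sizing assumed an unstratified comparison.

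**2. Why the pooled test is conservative.** With stratum shares w and risks p_k,

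p̄(1−p̄) = Σw·p_k(1−p_k) + Σw(p_k−p̄)².

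Blocking removes the last term from the difference between arms, but the pooled test still counts it. If that term is a share f of the total, the true two-sided error is 2[1 − Φ(1.96/√(1−f))]. With strata 60:40 (assumed):

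- Risks 20% and 30%: f = 0.24 × 0.10²/(0.24 × 0.76) = 0.013; error about 0.049.
- Risks 10% and 50%: f = 0.24 × 0.40²/(0.26 × 0.74) = 0.20; error about 0.028.

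**3. Power at the plan's rates.** This was simulated with 40,000 trials per scenario, 153 per arm, exact 1:1 balance within strata and a common treatment odds ratio. Marginal rates were 21.4% vs 9.4%. Layouts were two strata at 50/50 or 80/20, and three centres at 40/30/30. The odds ratio between extreme strata is assumed.

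| Between-stratum odds ratio | Gain from CMH (points) | Type I error, chi-square |
|---|---|---|
| 1 | −0.1 | 0.047 to 0.051 |
| 1.5 | 0 to 0.1 | 0.047 to 0.051 |
| 2 | 0.2 to 0.4 | 0.047 to 0.051 |
| 3 | 0.7 to 0.8 | 0.045 to 0.047 |
| 5 | 1.3 to 1.8 | 0.039 to 0.042 |
| 10 | 2.3 to 3.9 | 0.028 to 0.038 |

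The error column gives rounded ranges over the scenarios with a 21.4% control rate. CMH held 0.048 to 0.053. For 21.4% vs 6.4% the gain is at most 0.6 points.

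**4. Power at other assumed risks.** The settings are 167 per arm, strata 60:40 and a treatment odds ratio of 0.5.

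| Stratum risks (control) | Odds ratio between strata | Chi-square | Mantel-Haenszel |
|---|---|---|---|
| 20% / 30% | 1.7 | no material difference | |
| 15% / 30% | 2.4 | 0.615 | 0.625 |
| 20% / 40% | 2.7 | 0.713 | 0.726 |
| 25% / 50% | 3.0 | 0.767 | 0.786 |
| 30% / 60% | 3.5 | 0.797 | 0.822 |
| 10% / 50% | 9 | 0.58 | 0.65 |
| 10% / 60% | 13.5 | 0.54 | 0.66 |

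**5. A higher control rate.** At an assumed 40% with a 12-point difference and 153 per arm, the gain is 0.5 to 1.0 points at an odds ratio of 2, 1.9 to 2.8 at 3, 3.7 to 5.1 at 5, and 7.2 to 9.6 at 10.

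**The case against.** The best defence is that the planned test does what the plan sized it for. It is valid, its error is at or below 5%, and the stated power was computed without strata. The outcomes it covers are secondary, and section 3.9.2 already says composite 3 cannot be powered. All of this stands.

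Trimester may also be a weak stratum. The Protocol enrols women "intending to deliver at one of the study hospitals with gestational age < 16 weeks", so at entry it would separate the first from the early second trimester only. This holds in part: section 3.2.1 also accepts sleep testing at 24 to 28 weeks as a route to qualify, so the real spread is unclear.

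The 21.4% base rate is not a firm anchor. It comes from one hospital's deliveries and includes gestational diabetes, which the Protocol dropped from composite 2. The trial enrols high-risk women, so the rate could be higher; hence step 5.

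For the primary outcome, a change score already cancels stable stratum differences in DBP level. Only differences in change matter, and the documents give no figure for those.

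A reader might go further in three ways that the documents do not support:

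- **That power is certainly lost, by 7 points or more.** This needs strongly prognostic strata, and no risk by trimester or hospital is given.
- **That hospital stratification is being discarded in the Protocol.** Hospital is a stratification factor only in the Combined protocol and SAP.
- **That the logistic model already repairs the mismatch.** It is described as an analysis of predictors, with unnamed covariates. It could include the factor, but the text does not say so.

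**Conclusion.** The mismatch between design and analysis is real and applies to the primary DBP test as well as the categorical outcomes. The consequence is a possible, usually small, loss of efficiency, with no inflation of false positives.

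Under the assumed stratum effects, the loss of power is about 0 points below an odds ratio of 2 and roughly 1 to 2.5 points around 2.5 to 3.5. It reaches 7 to 12 points only at about 9 to 13.5 in the step 4 design. At the plan's 21.4% vs 9.4% it stays at 2 to 4 points even at an odds ratio of 10. The loss for the primary outcome cannot be sized from the documents.

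This is a free improvement: worth making because it costs nothing, but not a reason to doubt the planned tests.

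**What to change.** 1. Reconcile section 3.3 of the two documents and state which factor the randomisation list actually used.
2. In section 3.10.4, make the treatment comparison for the composites and the commoner individual outcomes a CMH test, with a Mantel-Haenszel risk difference and risk ratio, stratified by that factor.
3. Replace the plain t-test on DBP change with a linear model containing arm and that factor.
4. Keep the unstratified chi-square as a sensitivity analysis and Fisher's exact test for rare outcomes. At the hospital-wide 1.2% quoted for severe pre-eclampsia, eclampsia or HELLP, 167 per arm gives about 2 events per arm (0.012 × 167 = 2.0), too few for a stratified model to be dependable.
5. Adjustment for hospital, where it is not the stratification factor, is optional.

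The cost is wording only. The factor was needed to randomise, so it should already be recorded. When strata are not prognostic, the stratified test gives up about 0.1 points of power in the step 3 scenarios. If the arms have already been compared, the stratified results should be labelled as added afterwards.

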1.3 Research Objectives

1.3.1 **Primary Objective:** To compare whether the treatment effect of CPAP on SDB during pregnancy can improve blood pressure control in high risk pregnancy

- Systolic/diastolic blood pressure during daytime ANC at 10:00-12:00 am at randomization (GA 0-16 week), 1.5-2 month after randomization (GA 18-20 week), and 3-4 month after randomization (GA 24-28 week), 5-6 month after randomization (GA 32-34 week) and monthly (GA>35 week) until delivery

1.3.2 **Secondary Objective:**

- To compare the composite outcome of pre-eclampsia/GHT, GDM, fetal growth restriction, and pre-term labor between the CPAP treatment and control groups. And individual outcomes.
- To compare the night-time blood pressure compared to control group. 2nd outcome

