3.6.1.2 Second trimester

- Routine ultrasound at 18-20week gestation
- OGTT screening for GDM at 24-28week gestation
- 24-28week gestation: optional ultrasound depending on obstetrician's clinical decision
- Repeat blood test including fasting HbA1C, fasting blood sugar, complete blood count, and serologic blood test (anti-HIV, VDRL, Rh blood group)
- Urinary analysis

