3.7.2 Control Group

- Subjects will receive standard antenatal care and follow-up plan similar to the intervention group.

Primary outcome

- Systolic and diastolic blood pressure, which will be measured at rest using sphygmomanometer twice on both arms by research nurses during daytime ANC at 10:00-12:00 pm at randomization (GA 0-16 week), 1.5-2 month after randomization (GA 18-20 week), and 3-4 month after randomization (GA 24-28 week), 5-6 month after randomization (GA 32-34 week) and monthly (GA>35 week) until delivery

Secondary outcome

- 24-hour ambulatory blood pressure monitoring (daytime versus night time) using the non-invasive technique from pulse transit time (SomnoTouch NIBP).
- Pregnancy complication listed as composite endpoints below

(Composite endpoint): A combination of clinical endpoints in maternal and fetal outcomes, data from Ramathibodi hospital during 2013-2014) *

- **Composite 1:** hypertensive disorder of pregnancy;
- **Composite 2:** hypertensive disorder of pregnancy or preterm labor or fetal growth restriction
- **Composite 3:** Preterm labor or fetal growth restriction, or severe pre-eclampsia or eclampsia or death; (composite 3 incidence=10%)

*Given that the incidence of hypertensive disorder incidence= $136/3787=3.6\%$;
gestational diabetes incidence= $601/3787=15.9\%$; fetal growth restriction incidence= $157/3787=4.1\%$; preterm labor incidence=10%; and severe pre-eclampsia/eclampsia/HELLP syndrome incidence= $(43+ 1+3=46/3787=1.2\%)$, respectively.

- Individual component of the composite endpoints including incidence of hypertensive disorder of pregnancy, gestational diabetes, preterm labor, and fetal growth restriction
- Glucose level, Oral Glucose Tolerance Test (OGTT), HbA1C
- Fetal ultrasound results: uterine Doppler arterial blood flow, fetal growth restriction
- Neonatal outcome: birth-weight, APGAR score, Length of stay, NICU admission

- Placenta character: weight will be measured at birth by the neonatal nurse.

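### The reason given for leaving gestational diabetes out of the endpoint analyses fits only women with diabetes at entry, and the Protocol still lists it as an outcome

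*Protocol*

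**What the plan says.** - **Exclusion.** Protocol 3.10.4: "Gestational diabetes, as one of the inclusion criteria, was not included in endpoint analyses as initially planned". Section 3.10.4 of the Combined protocol and SAP, which its timetable suggests is the earlier version, has no such sentence.
- **Entry.** Protocol 3.2.1 requires women to "Have been diagnosed as high-risk pregnancy by obstetricians by having any of the following conditions", followed by items a to e. Item e is "Having diabetes mellitus or history of gestational diabetes in previous pregnancy"; the Combined protocol and SAP has the same item. Items a to d cover chronic hypertension, hypertension before 20 weeks, pre-eclampsia or gestational hypertension in a recent pregnancy, and pre-pregnancy obesity.
- **Timing.** Women are at their first antenatal visit, "intending to deliver at one of the study hospitals with gestational age < 16 weeks". Protocol 3.6.1.2 schedules "OGTT screening for GDM at 24-28week gestation".
- **Objective.** Protocol 1.3.2: "To compare the composite outcome of pre-eclampsia/GHT, GDM, fetal growth restriction, and pre-term labor between the CPAP treatment and control groups".
- **Outcomes.** The secondary outcome list under Protocol 3.7.2 keeps "Individual component of the composite endpoints including incidence of hypertensive disorder of pregnancy, gestational diabetes, preterm labor, and fetal growth restriction", and separately keeps glucose, OGTT and HbA1C. Composites 1 and 2 in that list do not contain GDM. In the Combined protocol and SAP both do, with stated incidences of 18.5% and 21.4%.

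**The concern.** An outcome fixed in part by the entry criteria cannot show a treatment effect in the women concerned, so the general idea behind the sentence is sound. The difficulty is that the criterion is not GDM in the current pregnancy. It is diabetes mellitus, or GDM in an earlier pregnancy, and a woman can qualify without either. Followed as written, 3.10.4 drops a planned outcome for all women on a reason that covers only some of them.

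Two things are at stake. First, a reader cannot tell from the Protocol whether GDM will be compared between arms. Second, the trial is open-label, and the change carries no date and no statement of whether outcome data had been seen. A change to a planned outcome in that setting needs a reason that agrees with the protocol's own criteria.

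**Working it through.** Most of this check compares text; the arithmetic gives the size.

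**1. Does the criterion match the reason?**

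| Woman enters by | Can she have new GDM in this pregnancy? | Does the stated reason apply? |
|---|---|---|
| Item e, diabetes mellitus | No | Yes |
| Item e, previous GDM only | Yes | No; this is history, not the outcome |
| Items a to d only | Yes | No |

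**2. Timing.** Booking is before 16 weeks and the OGTT is at 24-28 weeks, so for a woman randomised near booking GDM arises after randomisation. This may not hold for all: 3.2.1 lets sleep-disordered breathing be established at 24-28 weeks, and 3.3 stratifies randomisation by trimester. Some women may be randomised around or after the OGTT.

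**3. Is the reason applied evenly?** Items a to c are hypertension or a history of pre-eclampsia or gestational hypertension, yet hypertensive disorder of pregnancy is kept and forms the whole of composite 1. A history of pre-eclampsia stands to hypertensive disorder as a history of GDM stands to GDM.

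**4. Where GDM now stands in the Protocol.** Present: objective 1.3.2 and the individual outcomes under 3.7.2. Absent: composites 1 and 2 under 3.7.2. Excluded: the endpoint analyses in 3.10.4.

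**5. The plan's own rates** (hospital data, 2013-2014, all deliveries):
- GDM: 601/3787 = 15.9%
- preterm labor: 10% as stated
- growth restriction: 157/3787 = 4.1%
- hypertensive disorder: 136/3787 = 3.6%
- composite 1 with GDM: 699/3787 = 18.5%
- composite 2 with GDM: 812/3787 = 21.4%

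These reproduce. GDM is present in 601/699 = 86% of the composite 1 events. The overlap with hypertensive disorder is 136 + 601 − 699 = 38, so removing GDM removes 699 − 136 = 563 events (563/699 = 81%) and leaves 3.6%. For composite 2, GDM accounts for up to 601/812 = 74%.

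**6. What a GDM analysis could show.** Assume a control rate of 15.9% and a halving to 7.95%, two-sided 0.05. The halving is an assumption for illustration; the documents state no effect on GDM.

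Power = Φ{[δ√n − 1.96√(2p̄(1−p̄))] / √(p₁(1−p₁) + p₂(1−p₂))}

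With δ = 0.0795, p̄ = 0.11925 and n = 153 per arm (the figure used in 3.9.2): (0.983 − 0.898)/0.455 = 0.187, so power is 0.57. For 80% power, 260 per arm would be needed. The share of women who would be left out is not in the documents; over an assumed range:

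| Share left out | n per arm | Power |
|---|---|---|
| 0% | 153 | 0.57 |
| 10% | 138 | 0.53 |
| 20% | 122 | 0.48 |
| 30% | 107 | 0.43 |
| 40% | 92 | 0.38 |

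The comparison would be an estimate with a confidence interval, not a decisive test.

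**The case against.** The strongest reply is that the reason is incomplete rather than wrong. Item e does admit women with diabetes mellitus, and they cannot develop GDM. That stands, and it supports restricting the analysis to women without diabetes at entry. It does not reach the other women.

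Second, the phrase about endpoint analyses may mean only the composites. The secondary outcome list uses the term for them, and GDM survives in the individual list. This reading is plausible and would shrink the point to the composites plus wording. But 3.10.4 does not say so, and 1.3.2 still puts GDM in the composite, so the sections disagree on either reading.

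Third, the hypertension parallel is imperfect. Under the definitions in 2.1 a woman with chronic hypertension can still have a new event, superimposed preeclampsia; a woman with diabetes has no counterpart. That is right for pre-existing disease. It does not answer the parallel between a history of GDM and a history of pre-eclampsia.

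Fourth, glycaemic outcomes survive: glucose, OGTT and HbA1C stay listed, and 3.10.4 analyses glucose level with a mixed model. A reader might infer that objective 1.3.2 is left unanswered. It is not, because hypertensive disorder, growth restriction, preterm labor and night-time blood pressure are still compared; only the GDM part is in doubt.

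Fifth, a reader might infer selective reporting from the past tense. The documents do not support that. The change is stated openly, past tense also appears in 3.3, and nothing shows that the decision followed sight of the data. The sentence about reporting to the ethics committee follows the interim-analysis item and may or may not cover this change.

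**Conclusion.** The point stands in a limited form. The stated reason justifies leaving out women with diabetes at entry, not dropping index-pregnancy GDM for everyone. It is applied unevenly, and the Protocol contradicts itself on whether GDM is an outcome. Only secondary outcomes are affected; the primary blood pressure comparison is untouched.

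On the plan's figures GDM is the commonest complication listed (15.9%) and was present in 86% of composite 1 events. Those rates are hospital-wide and come from before the trial, so they show relative weight and do not predict rates in this high-risk cohort. The share of participants with diabetes at entry is unknown.

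It would go too far to say that GDM is a post-randomisation outcome in every woman: 3.2.1 and 3.3 leave room for late randomisation. The transparency point is only that this is an undated change in an open-label trial.

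**What to change.** 1. Replace the sentence in Protocol 3.10.4. Analyse GDM as an individual secondary outcome, by randomised arm, in women without diabetes mellitus at entry and not yet tested for GDM at randomisation. Both conditions are known at randomisation, so the comparison stays randomised.
2. Report composites 1 and 2 with GDM, as planned in the Combined protocol and SAP, in the same subset and as supportive only.
3. Reconcile the test that defines GDM. Protocol 2.1 describes a two-step 50-g then 100-g procedure, while 3.5.4 refers to a 75-g OGTT. The text should say which governs the outcome.
4. Align 1.3.2, the outcome list under 3.7.2 and 3.10.4.
5. State when and why the change was made, and whether outcome data had been seen.

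The cost is a few table rows, from a test already scheduled; the documents do not show how complete the results are. The subset is smaller than the full cohort, and power is modest on the assumptions above. It also adds a few secondary comparisons at an unadjusted 0.05, so these rows should be presented as estimates with intervals.

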3.9 Sample size estimation

3.9.1 Based on primary outcome

Power	Alpha	SD	Mean difference	M (Intervention /control)	Intervention N	Control N	Total N
0.80	0.05	7.4	2.0	1	216	216	432
0.80	0.05	7.4	2.5	1	139	139	278
0.80	0.05	7.4	3.0	1	111	111	222
0.80	0.05	7.4	3.5	1	71	71	142

Sample size calculation will be based on the primary outcome, which is the reduction in blood pressure. Based on the previous data by Reid, et al the mean diastolic blood pressure during pregnancy approximates 92.7 ± 7.4 mmHg [50]. Type I & II error and a ratio of intervention versus control are set at 0.05, 0.2, and 1:1, respectively. Estimated sample sizes are display below according to level of mean differences.

A systematic review and meta-analysis showed that CPAP could reduce blood pressure in OSA patients of -2.87 (95%CI -5.18-0.55) [25]. We, therefore, set mean difference of at least 2.5 mmHg, which will require 278 subjects to enroll. Taking into account for loss to follow-up of 20%, a total of 334 subjects are required (167 each arms). Additional number of subjects to be recruited was increased during January 2019-May 2019 up to 360 cases to allow for the potential subject discontinuation of the study with approval of the ethic committee.

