#### **3.10.4 Statistical analysis**

- Baseline demographic and clinical variables will be summarized using mean and its standard deviation (SD) or median and inter-quartile range as appropriate for continuous data, whereas categorical variables are summarized in frequencies and percentage. Comparisons of baseline characteristics between the 2 groups will be performed using *t*-test for the continuous variables and  $\chi^2$  test for the categorical variables.
- A blinded evaluation is planned to assess the observed primary end point by a clinical outcome assessment committee.
- The null hypothesis of the primary outcome for the  $\Delta$  change of blood pressure (DBP) between treatment and controls are tested at 2-sided significant level of *p*-value <0.05 using *t*-test.
- Analyses for repeated measurement of secondary outcomes for continuous variables such as 24-hour blood monitoring, glucose level, Uterine artery Doppler ultrasound pulsatile index, estimated fetal growth, at 6-8 weeks after randomization, and during 2-3rd trimesters compared to baseline are performed using a longitudinal data analyses with linear mixed model.

- Analyses of secondary outcome of categorical data such as composite outcome 1 to 3, and individual outcome, control of BP, or non-dipping BP pattern will be compared between CPAP and control groups using  $\chi^2$  test, or Fisher exact test as appropriate.
- Predictors for composite outcome, and individual outcomes will be analyzed with multivariate logistic regression model adjusting for other co-variates.
- Statistical analyses will be performed according to the intention-to-treat analysis. Per-protocol analysis will then be analyzed for the comparisons of the results.
- Missing data will be handled with data imputation technique.
- All statistical analyses are considered significant at the threshold level of 2-sided p-value  $< 0.05$ . Statistical analyses are performed using STATA Version 13.1 (StataCorp, College Station, TX).

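### The primary DBP test is labelled intention-to-treat, but it is an unimputed t-test on change that leaves out randomised women without the needed reading, with no missing-data sensitivity analysis

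*Protocol*

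**What the plan says.** Four statements in the Protocol bear on this point.

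- **Population (3.10.4):** "Statistical analyses will be performed according to the intention-to-treat analysis". A per-protocol analysis follows for comparison. Per-protocol and as-treated analyses with instrumental-variable regression are added for protocol violations.
- **Primary test (3.10.4):** "The null hypothesis of the primary outcome for the Δ change of blood pressure (DBP) between treatment and controls are tested at 2-sided" significance of 0.05 by t-test.
- **Missing data (3.10.4):** "We did not apply imputation for missing data because they were not used for the analysis".
- **Planned loss (3.9.1):** "Taking into account for loss to follow-up of 20"%, which takes 278 women to 334. Enrolment was later raised to as many as 360 to allow for discontinuation.

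DBP is a repeated measurement. The primary outcome under 3.7.2 lists readings at randomisation and at GA 18-20 and 24-28 weeks, and then "5-6 month after randomization (GA 32-34 week) and monthly (GA>35 week) until delivery". For repeated continuous secondary outcomes, the same analysis section already has a method: they "are performed using a longitudinal data analyses with linear mixed model".

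The Combined protocol and SAP (3.10.4) says something different on missing data: "Missing data will be handled with data imputation technique". It names no technique.

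**The concern.** A change score needs two readings. With no imputation and no model that borrows from a woman's other visits, anyone without one of the two drops out of the primary comparison, although she was randomised. That does not sit with the intention-to-treat label. The reason given is also circular: the values were not imputed because they were not used.

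The choice matters because absence need not be random. The trial is open-label. The Protocol's reasons for ending participation in the allocated arm (3.10.5) include severe preeclampsia, eclampsia and HELLP syndrome, which are tied to blood pressure, and readings run only until delivery. If such women also lack later readings, those who remain are a selected group, and the selection may differ between arms. The per-protocol, as-treated and instrumental-variable analyses deal with protocol violation. They do nothing for a missing outcome.

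Because no visit is named for the change, the set of excluded women is also open. A change to GA 18-20 weeks would lose few women; a change to the last weeks before delivery could lose many more.

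**Working it through.** **Inputs from the Protocol, 3.9.1.** SD 7.4 mmHg; target difference 2.5 mmHg; two-sided alpha 0.05; power 0.80; 1:1 allocation; 278 evaluable (139 per arm); 20% loss; 334 after inflation; later up to 360. Section 3.10.6 sets 30% loss as a stopping level.

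**Step 1: the plan's own figure.** n per arm = 2 × (1.960 + 0.842)² × 7.4² / 2.5² = 137.5, so 138 by the normal approximation and 139 by the noncentral t. The stated 139 per arm reproduces. The 334 is 278 × 1.2 = 333.6; dividing by 0.8 instead gives 347.5, so 348.

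**Step 2: power if women without the reading are left out.** Power to detect 2.5 mmHg, normal approximation:

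| Enrolled | Share excluded | Analysed | Power |
|---|---|---|---|
| 334 | 20% | 267 | 0.79 |
| 360 | 20% | 288 | 0.82 |
| 334 | 30% | 234 | 0.73 |
| 360 | 30% | 252 | 0.76 |

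At the planned loss, power stays near 0.80, so it is not the main problem.

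**Step 3: bias.** Let p be the share missing in an arm, and k the amount by which the mean DBP change of missing women is worse than that of observed women. The observed mean in that arm is then better than its all-randomised mean by p × k. The shift in the estimate in favour of CPAP is

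p(CPAP) × k(CPAP) − p(control) × k(control).

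The documents give neither p by arm nor k, so the values below are assumptions.

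| Missing, CPAP | Missing, control | k, CPAP (mmHg) | k, control (mmHg) | Shift |
|---|---|---|---|---|
| 25% | 15% | 4 to 6 | same | 0.4 to 0.6 towards CPAP |
| 15% | 25% | 4 to 6 | same | 0.4 to 0.6 towards control |
| 30% | 10% | 4 to 6 | same | 0.8 to 1.2 towards CPAP |
| 20% | 20% | 4 to 6 | same | 0 |
| 20% | 20% | 2.5 to 5 | 0 | 0.5 to 1.0 towards CPAP |

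For example, (0.25 − 0.15) × 4 = 0.4 and (0.25 − 0.15) × 6 = 0.6 mmHg, which is 16% to 24% of 2.5.

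**Step 4: effect on the test, first row.** With 360 enrolled, 180 × 0.75 = 135 and 180 × 0.85 = 153 women are analysed. The standard error is 7.4 × √(1/135 + 1/153) = 0.874 mmHg. With no true effect, a shift of 0.4 to 0.6 mmHg raises the two-sided type I error from 0.05 to about 0.07 to 0.11.

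**The case against.** The strongest reply is that the text is thin and should not be read for more than it says.

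- A reader might infer that every woman with any missing value is dropped and that the primary result is a completers-only comparison. The Protocol says only that missing data were not used. With no visit named, a woman lost in late pregnancy may still count if an earlier reading defines the change. The mixed model for secondary outcomes can also keep women with partial follow-up.
- A reader might take 20% of 360 as 72 women excluded. The 20% is a planning allowance for loss to follow-up, applied to get from 278 to 334. It is not a count of missing readings.
- Stopping CPAP, or leaving the allocated arm under 3.10.5, is not the same as having no blood pressure reading. Antenatal visits follow usual care (3.11) and become more frequent in the third trimester (3.6.1.3), so DBP may well be recorded for these women.
- The size of the bias rests on assumed loss patterns, and its direction is unknown. If CPAP works and more controls are lost with severe disease, the estimate moves against CPAP.

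All four stand, and they limit the point to an available-case analysis whose bias may be nil or of either sign. They do not remove it. Under any choice of visit, the t-test excludes randomised women without that reading, and nothing planned tests how much this matters.

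**Conclusion.** The concern holds as an available-case problem. The Protocol attaches an intention-to-treat label to a primary test that leaves out randomised women without the needed DBP reading, does not define the visit, plans no missing-data sensitivity analysis, and departs from the imputation foreseen in the Combined protocol and SAP without an adequate reason.

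The risk is bias more than lost power. How large it is cannot be known from the documents. The 0.4-0.6 mmHg illustration depends on a 10-point difference in missingness and a gap of 4-6 mmHg, both assumed. The documents do not show that loss is differential or that it favours CPAP. The point still needs correcting because it concerns the primary result and a better method is already in the plan.

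**What to change.** 1. Analyse the primary DBP outcome with the linear mixed model already specified for secondary outcomes. Use all recorded DBP values of all randomised women, and adjust for the randomisation strata. Section 3.3 gives these as trimester in the Protocol and centre in the Combined protocol and SAP, so state which were used.
2. Name one primary visit or contrast. An arm-by-visit model otherwise gives several effects to choose from.
3. Add a sensitivity analysis, by multiple imputation or with a delta adjustment that makes missing values worse by stated amounts in each arm. The mixed model assumes missing at random, so it does not remove bias from losses that the recorded readings fail to predict; assumptions that depart from missing at random are the ones to vary. Neither document planned such an analysis, so present it as new.
4. Report missing DBP readings by arm and visit, with reasons. Count women who stopped CPAP but were still measured separately from women with no reading.
5. Reconcile the missing-data statements in 3.10.4 of the two documents. Keep the disclosure of what was originally done. The Protocol's past tense suggests that analysis may have begun; if outcome data have been seen, label the new primary model post hoc and show the t-test result beside it.

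The cost is SAP wording and modest extra analysis. No new data are needed.
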